Financial Burden and Health Insurance Among Survivors of Colorectal Cancer. Patients diagnosed with colorectal cancer have a higher risk of experiencing financial burden related to health care costs when compared to patients diagnosed with other types of cancer.⁹ While many cancer survivors report experiencing financial burden^{3,8}, financial burden is particularly acute among survivors of colorectal cancer.^{10,11} Outcomes of financial burden among colorectal cancer survivors include lower health related quality of life, employment concerns, and delay or lack of engagement in needed surveillance and follow-up care.¹⁰⁻¹² Type of health insurance, which may be related to offsetting of burdensome medical costs, has been shown to be related to engagement in follow-up and surveillance care among colorectal cancer survivors.¹³ Private health insurance, for instance, has been shown to be a protective factor for receipt of surveillance care among colorectal cancer survivors. Low health insurance literacy has also been linked with a higher degree of financial burden among colorectal cancer survivors.¹⁴ This obligates practitioners and interventions to target health insurance literacy among this population to reduce financial burden and improve adherence to needed cancer surveillance and follow-up care.

Previous Study

In 2018, the American Cancer Society funded a project to develop and pilot a health insurance navigation intervention with childhood cancer survivors from the Childhood Cancer Survivor Study (Protocol # 2018P003088- “Understanding and Improving the Health Insurance Coverage Among Long Term Follow-up Study Cohort Participants”. The present study builds on the project to adapt the intervention for adult survivors of colorectal cancer.

Rationale of Proposed Research

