Health care reform under the Patient Protection and Affordable Care Act (ACA) offers considerable opportunities for colorectal cancer survivors to obtain coverage and improve access to needed care. However, in the general population, many people have low understanding of available insurance benefits and resources and have limited health insurance literacy (i.e. perceived knowledge, ability, and confidence to make informed decisions about choosing and using health insurance).¹⁵ Misperceptions about which services require out-of-pocket costs may lead some enrollees to avoid services that are in fact exempt from cost sharing. For colorectal cancer survivors are particularly vulnerable to financial burden related to low health insurance literacy.¹⁴ For colorectal cancer survivors, having a proficient understanding of health insurance is necessary for obtaining adequate health insurance to meet follow-up and surveillance needs without experiencing a significant degree of financial burden

2. Specific Aims and Objectives

Aim 1: To conduct an open pilot of a videoconferencing-based randomized trial of the health insurance navigation tools program with approximately 5 colorectal cancer survivors.

A1a: To assess the preliminary feasibility and acceptability of the HINT intervention via the measures and methods described below

A1b: To utilize open pilot feasibility and acceptability data to inform Aim 2 (RCT) methodology

Aim 2: To conduct a videoconferencing-based randomized trial of the health insurance navigation tools program (HINT) (n= approximately 60).

A2a: To assess the feasibility (number of eligible enrolled and sessions completed) and acceptability (satisfaction, perceived support) of participants undergoing a health insurance navigation tools program (HINT).

A2b: At 3-month post-program follow-up, to assess the efficacy of the HINT to assist participants with accessing and utilizing coverage and managing costs. Primary outcomes are 1) health insurance literacy and 2) financial distress related to medical costs. A2b Hypothesis: The HINT, compared to enhanced usual care, will improve participants’ health insurance literacy and decrease financial distress.

3. General Description of Study Design

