Open Pilot Design: We will recruit approximately 5 colorectal cancer survivors from Massachusetts General Hospital via the Research Patient Data Registry (RDPDR) to take part in a health insurance navigation intervention. Recruitment, consent, and intervention approach for the pilot will mirror the trial design, as described below. The purpose of the open pilot is to inform any changes in the trial and program approach prior to implementing the randomized pilot trial.

Randomized Trial Design: We will recruit and randomize approximately 60 colorectal cancer survivors from Massachusetts General Hospital via the Research Patient Data Registry (RDPR) to a health insurance navigation intervention or to enhanced usual care (Please see Sections III and IV for information on subject selection and consenting procedures). We have selected this sample size of approximately 40 per arm to enable evaluation of feasibility and acceptability goals as well as explore meaningful differences in the outcomes.⁷⁸ Surveys will be conducted at baseline and 3-month post program completion follow-up via REDCap or mail. All participants will be asked to complete a follow-up survey approximately 3-months after the HINT intervention period (in other words approximately 5-months post pilot trial enrollment). Participants will be remunerated \$20 for each survey.

Study Arms

Enhanced Usual Care

Enhanced usual care will consist of a mailed or emailed copy of a health insurance booklet.

Navigation Intervention

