The intervention will be delivered via synchronous videoconferencing (real-time delivery and communication between the navigator and the participant) by a trained patient navigator (See Intervention Fidelity in Section VI) and will consist of 5, approximately 30-minute sessions delivered every week or two, over the span of approximately one month (See Table 1: Proposed HINP Intervention). The sessions will occur one-on-one between the navigator and the participant and will be interactive (i.e. participants will be able to ask questions and respond to content throughout the sessions). The proposed program content was informed by the following: 1) aforementioned research on the associations between financial burden and health insurance literacy among colorectal cancer survivors, 2) CCSS health insurance survey, 3) ACA provisions that are relevant to survivors (e.g., prevention services exempted from cost sharing, sources of available coverage and eligibility, benefits policies that have cost-related implications like OOP costs, and essential health benefits such as prescription medications), and 4) an ongoing randomized pilot trial of the program with survivors of childhood cancer. The navigation intervention group will also receive a mailed copy of the health insurance booklet given to the enhanced usual care arm.

Table 1: Proposed HINT Intervention
Session One: Learning About Survivorship Healthcare Needs
Sessions Two: Learning About Your Plan in Relation to Policy
Session Three: Navigating One's Own Plan
Session Four: Managing Care Costs

4. Subject Selection

Participants: Inclusion and Exclusion Criteria

Study participants will be identified via the online query tool of the RDPR for both the open pilot and randomized trial. Patients who are 1) **approximately** 6 months to 5 years posttreatment for stages I-III colon or rectal cancer or 2) **approximately** more than **3 months** post-diagnosis for stage IV colon or rectal cancer at the time of screening will be eligible. We will constrain records to patients who have (a) had a medical visit at a MGH Cancer Center (ie. MGH Boston, Danvers, Waltham or Mass General Cancer Center at Newton-Wellesley) in the past two years, (b) an ICD diagnostic code of colorectal cancer (i.e.,

malignant neoplasm of the colon, rectum, or rectosigmoid junction), and (c) a pathology report with the terms “stage I”, “stage one”, “stage II”, “stage two”, “stage III” or “stage three”.

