Potential participants will be identified via the Mass General Brigham RDPR. Patients among the Research Options Direct to You (RODY) designation within the RDPR will receive an opt-out letter from the study team. This letter (See Recruitment Letters) will describe the study procedures and ask patients to contact the study team within 3 days if they would not like to be contacted further about the study. Those who do not opt-out will be contacted via encrypted email or by phone by the PI or by a trained and CITI-certified research staff member, and they will be read or sent a brief description of the study (See Study Description Documents).

Patients may also express interest in the study by contacting the research team directly.

Patients who are interested will be screened for eligibility, and those who are eligible will undergo informed consent. Specifically, eligible and interested patients will be asked to review the study fact sheet by phone with a study team member. Once that is completed, the study fact sheet will be sent to participants in an encrypted / unencrypted email, depending on their preference (see HINT C Short Consent). This method of obtaining consent has been used in other IRB-approved trials, like 2018P000539). Following consent, enrollees will be assigned a unique study identification number and will complete a baseline assessment. Patients who consent and complete the baseline assessment will then be randomized into the intervention or control arm.

The study interventionist will contact consented participants randomized to the intervention via unencrypted or encrypted email to schedule the HINT sessions, again depending on patient preference. To facilitate communication with the oncology team, the interventionist will complete a summary documentation note within EPIC informing clinicians of the patients' participation in the program. We will send reminder notices via calls, emails, mail, and Patient Gateway for participants who have not completed the baseline survey or for those in the intervention arm who have not scheduled their sessions, as needed (see "HINT C Difficult to Reach Letter").

Privacy protection: To address security issues related to email communication, participants will be informed about security in the opt-out letter itself via inclusion of the following text:

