The patient navigator (PN) will undergo training by the Co-investigators and pilot sessions. The NCI, with support from the ACS, established the Patient Navigation Research Program (PNRP) to implement and evaluate patient navigator programs. The PNRP developed a navigation performance checklist with 3 quality indicators of care:^{17,18} 1) participant interaction (e.g., established rapport), 2) care management (assessed subjects' understanding), and 3) intervention delivery (e.g., relevant information provided on insurance options, cost savings). Study investigators will review approximately 15% of patient navigation encounters using these quality indicator criteria. Navigation sessions will be recorded following patient assent to facilitate these fidelity assessments. The recordings will be audio and not video.

Measures

To evaluate the pilot, we will use a mixed methods data collection approach, using both quantitative survey items and open-ended questions.²⁶ Most study measures will come from survey questions repeated from the 2011-2012 CCSS health insurance survey (see Appendix); some new questions will be added and are indicated as such. Survey development included modifications and inclusions of national survey questions²⁶⁻³² and a cognitive testing phase. Using data collected previously by the RDPR via abstraction of medical records, data will be used to provide information on cancer diagnosis, age at diagnosis, and cancer treatment. Data from the RDPR will provide information on sociodemographic and medical history since cancer treatment, and presence of a medical late effects and chronic health conditions including second cancers. The measures will include the following:

Participant Characteristic Measures (From RPDR and/or study surveys)

Characteristics: Age, Gender, Education, Race/Ethnicity, Partnership/Marital Status

Enabling Characteristics: Zip Code, Familiarity with ACA Policies

Health Insurance Literacy: Likert scale assessments of- Confidence in Understanding of Terms (e.g. Coinsurance), Confidence in Choosing, Comparing, and Using Insurance, Household and Personal Income

Cancer Diagnosis, Treatment Type

Outcome Measures

Primary Outcomes: Feasibility and Acceptability.

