1. Feasibility: Number of eligible enrollees and number of sessions completed. 2. Acceptability: 4-point scales of satisfaction with navigation services (To what extent has this program met your needs? Did you get the kind of health insurance assistance that you wanted? How helpful has this program been for you?) and perceived support (emotional/informational scale of the Medical Outcomes Study social support survey, an 8-item scale widely used with cancer patients).²⁰⁻²⁴

Secondary Outcomes: Efficacy.

The ACS's National Patient Navigator Leadership Summit recommend patient-navigation outcome measures, which include: perceived knowledge, perceived confidence in overcoming barriers to care, and satisfaction with patient navigation services. Accordingly, we will measure: 1) health insurance literacy, 2) financial distress related to medical costs, 3) familiarity with healthcare reform policies, 4) insurance status (among those insured at study enrollment), and 5) discussion with providers about health care costs²⁴ and preventive services among those having a visit during this interval (2-item y/n questions).

Secondary Outcomes: Program Satisfaction.

Program satisfaction outcomes will include Likert scale (very poor, poor, average, good, excellent) on items including communication with the navigator, scheduling convenience, number of sessions, length of sessions, the health insurance booklet, the overall quality of the program. Satisfaction with the virtual format delivery of the program will also be assessed on a Likert scale, and will include items on the MGB-approved video-conferencing system (ie. Zoom) and the material presented via PowerPoint during the navigation sessions. We will also assess likelihood of program recommendation for other colorectal cancer survivors (definitely would recommend, probably would recommend, neutral, probably would not recommend, definitely would not recommend). Program helpfulness will be assessed on a 1-10 scale. Lastly, open ended questions will be asked about helpfulness of the program and aspects of improve upon. Program satisfaction questions will be asked only of intervention arm participants.

7. Risks and Discomforts

Psychological Risks

Individuals may find it stressful to answer questions about their experiences with health insurance coverage and care. The risks associated with these discussions are minimal, and do not rise above the level of harm encountered during daily activities.

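### Secondary efficacy outcome 5 counts only participants with a visit in an unnamed interval that, on the survey schedule, follows randomization; no all-randomized comparison or visit rate by arm is planned

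*Combined protocol and SAP*

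**What the plan says.** Section 6 (Secondary Outcomes: Efficacy) lists five outcomes. The fifth is discussion with providers about health care costs "and preventive services among those having a visit during this interval (2-item y/n questions". No interval is introduced before that phrase. The grammar ties the visit restriction to the preventive-services item and leaves open whether it also covers the cost item. The fourth outcome is restricted too, but by a fact fixed at entry: "insurance status (among those insured at study enrollment".

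The plan has two surveys. The first precedes allocation (Section 5, Methods of Enrollment): "Patients who consent and complete the baseline assessment will then be randomized into the intervention or control arm". The second comes "approximately 3-months after the HINT intervention period (in other words approximately 5-months post pilot trial enrollment" (Section 3, Randomized Trial Design).

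Section 9 (Quantitative Data) includes provider communication in its examples of efficacy endpoints and plans chi-square and t-tests between the groups on preliminary efficacy outcomes. It also plans paired tests within groups and exploratory comparisons of other outcomes. It does not name outcome 5, give a denominator for it, or say how a participant without a visit is counted. It does not plan a visit rate by arm.

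On the instrument, Section 6 (Measures) says: "Most study measures will come from survey questions repeated from the 2011-2012 CCSS health insurance survey (see Appendix". That appendix is not among the documents reviewed.

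**The concern.** Randomization makes the arms comparable as randomized. It does not make the visitors in one arm comparable with the visitors in the other when the arm can influence who has a visit. If navigation brings in people who would otherwise have stayed away, the HINT visitors include a group with no counterpart among the control visitors. The difference in percentage discussing then mixes two things: whether navigation changes what people discuss, and whether it changes who is counted. Section 9's adjustment for baseline imbalances does not address selection that arises later.

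The protocol gives some reason to think attendance could move. The Section 1 background says interventions should target insurance literacy to "reduce financial burden and improve adherence to needed cancer surveillance and follow-up care". The program content draws on "ACA provisions that are relevant to survivors (e.g., prevention services exempted from cost sharing" (Section 3, Navigation Intervention). Section 9 lists intention to follow survivorship-care recommendations as an efficacy endpoint. Section 1 also says that misperceptions about cost "may lead some enrollees to avoid services that are in fact exempt from cost sharing", but that remark concerns the general population.

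What is at stake is the reading of one secondary outcome. Health insurance literacy and financial distress carry no visit restriction and are unaffected.

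**Working it through.** **Timing.** Two readings of the interval follow from the survey schedule:
- Baseline to follow-up survey, about 5 months from enrollment. The baseline survey comes just before randomization, so a visit in this window is in substance post-randomization.
- Program end to follow-up survey, about 3 months. This is wholly post-randomization.

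A fixed look-back in the survey wording could reach earlier. That cannot be checked.

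**Inputs.** The documents give no visit rate, discussion rate or target difference, so there is no stated figure to reproduce and every rate below is assumed. Let vC and vH be the visit rates in control and HINT, p the discussion rate in those who would attend anyway (50%, the same in both arms, so no true effect on discussion), and q the rate in visitors whom HINT induces (20% or 80%). HINT is assumed only to add visitors. Arm size n is taken as 30 and as 40, because the protocol gives both a total of 60 and 40 per arm.

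**Formulas.**
- Visitors-only rate in HINT: (vC × p + (vH − vC) × q) / vH
- Shift in the visitors-only difference: (vH − vC)/vH × (q − p)
- Standard error: √[p(1 − p)/(n·vC) + pH(1 − pH)/(n·vH)], with pH = p + shift
- Difference in visited-and-discussed among all randomized: (vH − vC) × q

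Example at 70%/90%: 0.20/0.90 × (0.80 − 0.50) = +0.067, and with q = 0.20 it is −0.067. At 50%/80%: 0.30/0.80 × 0.30 = 0.1125. The SE at 50%/80% with n = 30 is √(0.25/15 + 0.2373/24) = 0.163, so the ratio is 0.1125/0.163 = 0.69.

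| vC / vH | Visitors-only shift (points) | SE, n = 30 / 40 | Shift ÷ SE, n = 30 / 40 | All-randomized difference (points) |
|---|---|---|---|---|
| 95% / 98% | ±0.9 | 0.131 / 0.114 | 0.07 / 0.08 | +0.6 to +2.4 |
| 90% / 95% | ±1.6 | 0.134 / 0.116 | 0.12 / 0.14 | +1 to +4 |
| 80% / 90% | ±3.3 | 0.140 / 0.121 | 0.24 / 0.27 | +2 to +8 |
| 70% / 90% | ±6.7 | 0.145 / 0.125 | 0.46 / 0.53 | +4 to +16 |
| 50% / 80% | ±11.25 | 0.163 / 0.141 | 0.69 / 0.80 | +6 to +24 |

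**Direction.** The two measures can disagree in sign. At 60%/80% with p = 0.50 and q = 0.20, the visitors-only rate is 50.0% in control and (0.30 + 0.04)/0.80 = 42.5% in HINT, a difference of −7.5 points. Among all randomized it is 30.0% against 34.0%, or +4.0 points.

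**Limits.**
- The shift is zero if vH = vC with the same people attending, or if q = p.
- Equal visit rates alone do not guarantee zero. At 80% in both arms, with 10 points of attenders replaced (50% of those lost and 80% of those gained discussing), the shift is 0.10 × 0.30/0.80 = +3.75 points.
- The table is not an upper bound. At 50%/80% with p = 0.20 and q = 0.80 the shift is 0.375 × 0.60 = 22.5 points.

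**The case against.** A discussion with a provider presupposes a visit, so a visitors-only percentage is a natural thing to report. An item put only to visitors also needs a visit question or a skip, so visit counts by arm are probably obtainable; what is missing is a commitment to report them.

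Attendance may be high and hard to shift. Section 4 excludes the uninsured, requires a cancer-center visit in the past two years and admits stage IV patients from about 3 months after diagnosis. The upper rows of the table, with shifts of about 1 to 2 points, may then apply, and those are negligible at 30 or 40 per arm. The 50%/80% row needs a 30-point effect on attendance within about 5 months, which the documents do not support. Against that, two years is much longer than 3 to 5 months, and stage I–III patients may be up to about 5 years past treatment. The documents do not settle which row applies; visit rates by arm would.

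A reader might infer that better attendance is an aim of this trial. It is not: the Section 1 sentence is background on what interventions should target, and the Section 2 aims do not name attendance. A reader might also infer that the interval is certainly post-randomization. The survey schedule points that way, but the recall window is unseen, and its absence from the documents is not a fault in the plan.

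Finally, Section 9 does not repeat the visit restriction when it lists provider communication. That is silence on the denominator, not a planned all-randomized analysis; Section 6 has the only stated denominator.

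**Conclusion.** The point holds as a minor one with a cheap remedy. At least one item of outcome 5 has a denominator that, on the two schedule-based readings, depends on an event after randomization that the arm could influence. Neither an all-randomized comparison nor a visit rate by arm is planned.

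The documents do not show that HINT changes attendance or that the result will be biased. The size rests wholly on assumed rates: in the cases tabulated it runs from about 1 to 11 points in either direction, or about 0.07 to 0.80 standard errors across the two arm sizes.

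Outcome 5 is the last of five secondary efficacy measures in a pilot. It appears neither among the primary outcomes named in Aim 2b nor among those named in Section 6, and no decision rule uses it.

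**What to change.** **Section 6.** Define the interval as randomization to the follow-up survey. State whether the visit restriction covers both items. Confirm that the survey's visit question and recall window match.

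**Section 9.** Name outcome 5. Add a between-arm comparison, at follow-up only, of having had a visit in the interval and discussed the topic (no visit counts as no), in all randomized participants with a follow-up survey. Report the visit rate and the survey return by arm beside it. Keep the among-visitors result, with or without a test, labelled as conditional on a post-randomization visit.

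**Cost.** A sentence or two in each section, and a small survey edit if the recall window does not match. There are four downsides to state:
- The added measure combines attendance and discussion. With no effect on discussion among usual attenders it still shows +4 to +16 points at 70%/90% and +6 to +24 at 50%/80%, so it must be read with the visit rates and not taken alone as better communication.
- It scores a person with no visit due as a no.
- It has no baseline value, so the planned change scores and paired pre/post tests do not apply to it. Section 9 should say so.
- It still depends on survey return, itself a post-randomization event, which is why return is shown by arm.

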The consent form states that there may be no direct benefit to the participants from study participation. Participants in both groups will be given information that could improve their ability to access affordable coverage. Participants in the intervention group will also receive navigation support, for up to 5 video-based sessions. As an alternative to the intervention, participants may explore health insurance support options at their current primary care center.

9. Statistical Analysis

[name], and the study team at University of Utah will complete the analyses. The team will be blinded to treatment allocation until trial analyses completion. [name] team will receive de-identified study data.

Open Pilot

Pilot data is meant to inform and test the function of the study procedures, so no formal analyses will be performed. We will use preliminary feasibility and acceptability data (as outlined below) to inform necessary changes to our approach.

Randomized Trial

Quantitative Data

We will use descriptive statistics to report on the following endpoints: intervention feasibility (percent of participants enrolled), acceptability (satisfaction, perceived support) and efficacy (e.g., ACA familiarity, health insurance literacy, intention to adhere to recommended survivorship care, provider communication, and coverage status). Descriptive statistics will examine group differences at baseline; any imbalances will be adjusted. We will use chi square and independent t-tests to compare end-of-intervention changes in preliminary efficacy outcomes between the two groups. Although a 3-month post intervention follow-up period is brief, we will also conduct exploratory comparisons with other study outcomes to see if trends change in the expected direction. We will compare pre/end-of-treatment, within groups, with paired t-tests. In addition, we will use bivariate statistics to examine sociodemographic and cancer-related factors (e.g., type of diagnosis, age at diagnosis, cancer treatment¹⁸, cancer treatment (e.g., cranial radiation yes/no, anthracycline exposure yes/no) associated with feasibility, acceptability and preliminary efficacy outcomes.

10. Monitoring and Quality Assurance

Training of all Study Personnel in the Responsible Conduct of Human Studies

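### The analysis team cannot stay blinded until all analyses are complete, because it also analyses satisfaction data collected only in the intervention arm

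*Combined protocol and SAP*

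**What the plan says.** Section 9 (Statistical Analysis) assigns the work to one group: "and the study team at University of Utah will complete the analyses". It continues: "The team will be blinded to treatment allocation until trial analyses completion". The only data safeguard stated there is that the "team will receive de-identified study data".

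The endpoints listed for the randomized trial in that section are "intervention feasibility (percent of participants enrolled), acceptability (satisfaction, perceived support) and efficacy". Section 9 also plans between-group tests of the efficacy outcomes, and bivariate analyses relating sociodemographic and cancer factors to feasibility, acceptability and efficacy.

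Section 6 (Outcome Measures) defines the fields concerned. The program-satisfaction paragraph ends: "Program satisfaction questions will be asked only of intervention arm participants". The primary acceptability outcome is described as "Acceptability: 4-point scales of satisfaction with navigation services", together with a perceived-support scale. The primary feasibility outcome reads "Feasibility: Number of eligible enrollees and number of sessions completed".

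Under Study Arms in Section 3, the control arm receives a booklet and only the intervention arm receives navigation. Section 10 (Data Monitoring Plan) adds interim analyses throughout the trial without saying who performs them.

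**The concern.** A blinding statement that runs to the end of all analyses has to be compatible with every variable the blinded team handles. Here the team's remit includes variables that exist in one arm only, so a filled field discloses the arm.

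This matters because Section 9 leaves some choices until the data are seen. Baseline imbalances are to be adjusted for, but no covariates, threshold or model are named, and exploratory comparisons look for trends in a hoped-for direction. An analyst who knows the arms could, without intending to, make those choices in favour of HINT. Separately, a report that repeats the blinding sentence would describe a safeguard that the trial did not have.

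**Working it through.** The plan states no figure on this point, so there is none to reproduce. The check sets the sections side by side and then illustrates how far the blind would be lost.

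**Which fields reveal the arm**

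| Field | Arm in which it exists | Basis | Handled by the blinded team? |
|---|---|---|---|
| Program satisfaction | HINT only | Stated in Section 6 | Yes, on the natural reading of satisfaction in Section 9 |
| Acceptability: satisfaction with navigation | Apparently HINT only | Inferred: only HINT receives navigation (Section 3) | Yes, Section 9 |
| Sessions completed | HINT only | The control arm has no sessions (Section 3) | Inferred from Sections 2, 6 and 10; Section 9 gives feasibility only as percent enrolled |
| Perceived support | Not stated to be one-arm | Section 6 | Yes, but not part of this point |

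**Does the team need participant-level data?** Yes. Relating patient factors to acceptability requires each participant's satisfaction answers alongside that participant's covariates. An aggregate summary would not be enough.

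**Does de-identification help?** No. It removes names and record numbers and leaves the pattern of filled and empty fields intact.

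**Illustration of size**

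Inputs:
- *n* per arm is 30 (60 randomized, assumed split equally) or 40 (the per-arm figure in Sections 3 and 5). The mismatch between 60 in total and 40 per arm is a separate matter.
- *r* is the proportion of HINT participants with at least one satisfaction answer. The documents do not give it, so a range is shown.

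(a) *No group code in the file.* Classify anyone with an answer as HINT and everyone else as control. HINT participants identified = *n* × *r*. Share of all participants classified correctly = (*nr* + *n*) / (2*n*) = (1 + *r*) / 2.

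| *r* | Identified, *n* = 30 | Identified, *n* = 40 | Share classified correctly |
|---|---|---|---|
| 50% | 15 | 20 | 75% |
| 80% | 24 | 32 | 90% |
| 90% | 27 | 36 | 95% |
| 100% | 30 | 40 | 100% |

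(b) *A masked group code is present and linked to the satisfaction fields.* One answer decodes the label for all participants. With independent responses, the chance of at least one answer is 1 − (1 − *r*)^*n*:
- *r* = 10%, *n* = 30: 1 − 0.9^30 = 95.8%
- *r* = 10%, *n* = 40: 1 − 0.9^40 = 98.5%
- *r* = 50%, either *n*: above 99.99%

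The between-group tests need some group variable, so case (b) is plausible. The documents do not say how files are coded, merged or timed.

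**The case against.** The strongest reply is that the protocol is silent on data transfer, and silence is not a flaw. Nothing in it forbids sending efficacy data first, and names are removed from Section 9, so any division of roles cannot be fully read. This stands in part: blinding of the efficacy comparison alone could be preserved. It does not rescue the sentence as written, which extends the blind to the completion of the trial analyses and so covers the satisfaction analyses too.

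Three stronger readings are tempting and are not supported:
- A reader might infer that session counts certainly reach this team. Section 9 defines feasibility for analysis only as percent enrolled, so this is an inference.
- A reader might infer that every participant's arm is revealed. A HINT participant with no satisfaction answer (and no session record, if those are sent) is not identified directly. Decoding everyone requires a group code linked to the satisfaction fields, which the documents do not describe.
- A reader might infer that analyst blinding is the plan's declared protection for the efficacy comparisons and that all of those outcomes are self-reported. The plan says neither.

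It is also fair to say that the named tests are simple, that Section 9 calls efficacy preliminary, and that no effect on an estimate or error rate has been shown. Masking alone would not settle the open-ended baseline adjustment either; naming the covariates in advance is the direct remedy for that. These points limit the importance of the issue but do not remove the contradiction.

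**Conclusion.** The point holds in a limited form. Section 9 claims a blind that its own list of analyses breaks, because satisfaction data are collected in one arm and are needed at participant level. This rests on the explicit one-arm sentence in Section 6 and on the same team handling satisfaction. The acceptability items strengthen it by inference, and session counts would do so only if they are sent to the team.

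The extent of unmasking depends on the response rate and file structure: 75% to 100% of participants classified correctly for assumed response rates of 50% to 100% without a group code, and everyone if one answer is linked to a masked code. The consequence is possible analyst bias in the preliminary efficacy comparisons and an inaccurate blinding statement. It does not show that any result will be biased, and it has no bearing on bias from participants knowing their own arm.

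**What to change.** In Section 9:
1. Restate the blinding as lasting until the between-arm efficacy analyses are locked.
2. Release first a file with baseline data and both-arm outcomes under a masked arm code, without satisfaction, session or open-ended program fields. Complete and lock the between-arm efficacy analyses on that file.
3. Release the HINT-only fields after the lock, for the feasibility and acceptability analyses.
4. In Section 10, say who performs the interim analyses. If it is this team, apply the same separation to them; otherwise an early look at acceptability data would defeat the later split.

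This should be in place before the team first opens any HINT-only field, because unblinding cannot be undone. The cost is one extra export, a change of wording, and acceptability results that arrive slightly later. No participant procedure, outcome or sample size changes.
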